C	CECT CDD CR CRA eCRF CSM CT CTA CTCAE CV	contrast-enhanced CT Centre for Drug Development complete response Clinical Research Associate electronic case report form Clinical Study Manager computerised tomography clinical trial authorisation Common Terminology Criteria for Adverse Events coefficient of variation
D	3D Day DCE-MRI	3-dimensional calendar day Dynamic Contrast Enhanced- Magnetic Resonance Imaging
E	EANM EDC EFS EU	European Association of Nuclear Medicine electronic data capture event free survival European Union
F	FDA [¹⁸ F]FDG	U.S. Food and Drug Administration Fluorine-18 radiolabelled fluorodeoxyglucose
G	GCP G-CSF eGFR GMP GP	Good Clinical Practice granulocyte-colony stimulating factor estimated Glomerular Filtration Rate Good Manufacturing Practice General Practitioner
H	HCG HIV HRA	human chorionic gonadotrophin human immunodeficiency virus Health Research Authority
I	[¹²³ I] [¹²⁴ I] ICH GCP ICRP IMP INSS ITF IUD	Iodine-123 (radioactive isotope of iodine) Iodine-124 (radioactive isotope of iodine) International Conference on Harmonisation of Good Clinical Practice International Commission on Radiological Protection investigational medicinal product International Neuroblastoma Staging System Investigator Trial File Intra-uterine device
M	MBq MHRA m IBG MIP MRI mSv MUP-PET MYCN	megabecquerel Medicines and Healthcare products Regulatory Agency meta -iodobenzylguanidine maximum intensity projection magnetic resonance imaging milliSieverts (unit of ionising radiation) multi-wire proportional chamber position emission tomography v -myc myelocytomatosis viral-related oncogene
N	NAT	noradrenaline transporter

LIST OF ABBREVIATIONS AND DEFINITION OF TERMS

	Abbreviation	Definition
	NaI NCI NCRI CCLG NHS	Sodium iodide National Cancer Institute National Cancer Research Institute Children's Cancer and Leukaemia Clinical Studies Group National Health Service
P	PET PET/CT PI PSRB	positron emission tomography positron emission tomography/computerised tomography Principal Investigator Protocol Safety and Review Board
Q	QP	Qualified Person
R	REC R ₂ *	Research Ethics Committee transverse MRI relaxation rate (measure of intrinsic susceptibility MRI)

1 PROTOCOL SYNOPSIS

Full Title: A Cancer Research UK Phase I/II study to compare [¹²⁴I]meta-Iodobenzylguanidine (mIBG) positron emission tomography/computerised tomography (PET/CT) to [¹²³I]mIBG imaging in patients with metastatic neuroblastoma.

Short Title: A Phase I/II study of [¹²⁴I]mIBG PET/CT in neuroblastoma.

1.1 CLINICAL STUDY OBJECTIVES AND ENDPOINTS

Primary objective	Endpoint
1. To show that [¹²⁴ I]mIBG PET/CT can detect an equal or greater number of neuroblastoma lesions compared to conventional [¹²³ I]mIBG planar scintigraphy.	1. Comparison of the percentage of lesions detected as positive by [¹²³ I]mIBG planar scintigraphy which are also considered positive with [¹²⁴ I]mIBG PET/CT.

Secondary objectives	Endpoints
1. To show that [¹²⁴ I]mIBG PET/CT can detect an equal or greater number of neuroblastoma lesions compared to conventional [¹²³ I]mIBG scintigraphy with 3D imaging by SPECT (single photon emission computerised tomography).	1. Comparison of the percentage of lesions detected as positive by [¹²³ I]mIBG SPECT which are also considered positive with [¹²⁴ I]mIBG PET/CT.
2. Assessing the safety and toxicity profile of a single intravenous administration of [¹²⁴ I]mIBG.	2. Determining the causality of each adverse event to [¹²⁴ I]mIBG and grading severity according to National Cancer Institute Common Toxicity Criteria for Adverse Events (NCI CTCAE) version 4.02.

Tertiary objectives	Endpoints
[REDACTED]	[REDACTED]
[REDACTED]	[REDACTED]
[REDACTED]	[REDACTED]
[REDACTED]	[REDACTED]
[REDACTED]	[REDACTED]
[REDACTED]	[REDACTED]
[REDACTED]	[REDACTED]
[REDACTED]	[REDACTED]
[REDACTED]	[REDACTED]

Tertiary objectives	Endpoints

[REDACTED]
 
[REDACTED]
 
[REDACTED]
 
[REDACTED]
 
[REDACTED]
 
[REDACTED]
 
[REDACTED]
 
[REDACTED]
 
[REDACTED]
	
[REDACTED]
 
[REDACTED]
 
[REDACTED]
 
[REDACTED]
 
[REDACTED]

[REDACTED]
 
[REDACTED]
 
[REDACTED]
 
[REDACTED]
 
[REDACTED]
	
[REDACTED]
 
[REDACTED]
 
[REDACTED]
 
[REDACTED]
 
[REDACTED]

1.2 STUDY DESIGN

This is a multi-centre, non-therapeutic Phase I/II study directly comparing [¹²⁴I]mIBG PET/CT and conventional [¹²³I]mIBG imaging in patients with newly diagnosed, relapsed or refractory metastatic neuroblastoma. A minimum of 9 (if stopped after interim analysis) or 33 evaluable patients will be scanned at two centres in the UK.

Patients will be those who require routine conventional [¹²³I]mIBG planar scintigraphy as a means of assessing response to their ongoing treatment or for staging of their disease. The majority of patients will also be planned to undergo 3D imaging by SPECT where this is available. Eligible patients will undergo the planned routine [¹²³I]mIBG imaging as part of this study. These routine [¹²³I]mIBG planar scintigraphy findings will be reported by a Nuclear Medicine physician at the investigational site and will be used to confirm suitability for the subsequent novel [¹²⁴I]mIBG PET/CT imaging prior to administration of the novel [¹²⁴I]mIBG Solution for Injection.

The [¹²⁴I]mIBG PET/CT imaging will take place approximately 3-21 days after routine [¹²³I]mIBG imaging and before the commencement of any new anti-cancer therapy. Patients who fulfil the clinical criteria for [¹²⁴I]mIBG imaging in Section 4.1.3 will receive one injection of [¹²⁴I]mIBG and undergo imaging with [¹²⁴I]mIBG PET/CT the following day. Patients who do not fulfil these criteria will be withdrawn from the study. [¹²⁴I]mIBG PET/CT imaging undertaken as part of the clinical study will not affect the management or delay the commencement of new anti-cancer therapy of patients recruited to this study.

[¹²⁴I]mIBG PET/CT imaging data from the first patient will be analysed immediately by the Investigators to assess whether the scanning equipment specifications and scanning methodology are effective. The methodology will be adapted as required to ensure the quality of subsequent imaging data. Adaptations may also be made to resolve any practical and logistical issues with the events schedule for the next patient. Recruitment to the study will be competitive between centres. There is no minimum time interval required between patients.

The interim analysis will be performed after a minimum of 50 lesions have been identified by [¹²³I]mIBG planar scintigraphy from a minimum of 9 evaluable patients. If the number of lesions which were also identified using [¹²⁴I]mIBG PET/CT is less than 45 out of 50 the trial will be stopped early for futility. If all lesions (e.g. 50 out of 50) were also identified using [¹²⁴I]mIBG PET/CT the trial may be stopped early for efficacy. Otherwise recruitment will continue until a minimum of 100 lesions have been identified by [¹²³I]mIBG planar scintigraphy from a minimum of 33 evaluable patients.

All patients will be monitored for safety reporting from the time the patient / parent or guardian (as applicable) provides informed consent until their Off-Study assessment performed during a clinic visit or by telephone on Day 3 to 7 before the start of subsequent anti-cancer therapy. If there are any reported events considered to be related (highly probably, probably or possibly) to [¹²³I]mIBG and/or [¹²⁴I]mIBG still present at the Off-Study assessment, the patient will be followed by their Oncologist

until resolution, recovery to baseline, or stabilisation of these events, unless the patient starts another anti-cancer therapy.

Interpretation of imaging

The imaging review will be performed separately by an agreed number of observers who are Nuclear Medicine physicians experienced in the assessment of neuroblastoma. Two observers will be study Investigators and all others will be independent from the study to prevent subjective bias in the interpretation of the nuclear medicine *m*IBG scans. Lesions will be identified and scored by each observer using a diagnostic confidence level. The observers will review the lesions identified and where there is a difference in their separate scores they will return to the imaging in order to reach a consensus score. The number of lesions identified as positive by this scoring will be used to meet the primary objective of comparison of the novel [¹²⁴I]*m*IBG PET/CT modality with the recommended standard *m*IBG imaging modality for neuroblastoma which is [¹²³I]*m*IBG planar scintigraphy (see Section 9.1).

The majority of patients treated for neuroblastoma will have [¹²³I]*m*IBG scintigraphy using 3D SPECT over the chest and abdomen in addition to planar scintigraphy of the full body. The imaging review performed for the assessment of the primary objective will be repeated to read and score lesions identified by the available [¹²³I]*m*IBG SPECT. The number of positive lesions identified by SPECT will be used to meet the secondary objective of comparison of [¹²⁴I]*m*IBG PET/CT with [¹²³I]*m*IBG scintigraphy with 3D SPECT.

The imaging review will then be repeated to read and score all the available conventional imaging taken together including [¹²³I]*m*IBG planar and SPECT scintigraphy and cross sectional imaging with CT and MRI.

[Redacted]

[Redacted]

[Redacted]

[Redacted]

[Redacted]

[Redacted]

[Redacted]

[Redacted]

[Redacted]

[Redacted]

[Redacted]

[Redacted]

[Redacted]

[Redacted]

[Redacted]

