11 DEFINING THE END OF TRIAL

The 'end of trial' will be declared when one of the following is fulfilled:

- [¹²⁴I]mIBG Solution for Injection is considered too toxic to scan any further patients before the required number of patients have been recruited.
- Following the interim analysis, it is confirmed the trial is to stop due to futility as per Section 12.1 (end of trial will be the date of this decision).
- Following the interim analysis, it is confirmed the trial is to stop due to efficacy as per Section 12.1 (end of trial will be the date of this decision).
- If recruitment continues as allowed under the protocol beyond the interim analysis. Last Patient Last Visit is defined as the date when the last patient completes their participation in the trial, which will be either completion of the Off-study assessment or early withdrawal from the trial.

It is the responsibility of the CDD to notify the MHRA and the REC of the 'end of the trial'.

In cases of early termination of the study (for example, due to toxicity) or a temporary halt by the CDD, the CDD will notify the MHRA and the REC within 15 days of the decision and a detailed, written explanation for the termination/halt will be given. The entire study will be terminated when:

- [¹²⁴I]mIBG Solution for Injection is considered too toxic to scan any further patients before the required number of patients have been recruited.
- The stated minimum number of evaluable patients has been reached.
- The stated objectives of the study are achieved.

Regardless of the reason for termination, all data available for patients at the time of termination of the study must be recorded in the eCRF.

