12 DATA ANALYSIS AND STATISTICAL CONSIDERATIONS

12.1 SAMPLE SIZE

The primary endpoint of the study is the percentage of lesions identified as positive using [¹²³I]mIBG planar scintigraphy which are also identified as positive on [¹²⁴I]mIBG PET/CT. The definition of a positive lesion is described in section 9.1. The aim is to prove that there is more than 90% agreement between the methods, with an expected level of agreement of 97%. Patients are expected to have a median of 3 lesions. Lesions are assumed to be independent within patients for the primary analysis. The following two stage design will be used, where the true proportion of agreement is denoted by P:

In the first stage, a total of at least 9 patients will be recruited, with a combined total of at least 50 lesions positive on [¹²³I]mIBG. Initially an exact one-sided binomial test of the null hypothesis: $P \geq 97\%$ will be done using $\alpha = 0.05$. If this is rejected in favour of the alternative hypothesis $P < 97\%$, the trial will be stopped early for futility. With a total of exactly 50 lesions this will occur if 45 or fewer lesions are also positive on [¹²⁴I]mIBG PET/CT.

If the null hypothesis is accepted, a further one-sided binomial test of the null hypothesis: $P \leq 90\%$ will be done using $\alpha = 0.025$. If this is rejected in favour of the alternative hypothesis $P > 90\%$ then the trial may be stopped early for efficacy. With a total of 50 lesions this will occur only if all 50 lesions are also positive in [¹²⁴I]mIBG PET/CT. If this null hypothesis is not rejected, the trial will continue to the second and final stage.

The second stage will end when an overall total of at least 33 patients with at least 100 lesions have been recruited. An exact one-sided binomial test of the null hypothesis: $P \leq 90\%$ will be done using $\alpha = 0.025$. If this is rejected in favour of the alternative hypothesis $P > 90\%$ then the trial will be declared a success. With a total of 100 lesions this will occur if at least 96 lesions are also positive on [¹²⁴I]mIBG PET/CT.

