Overall this design has 82% power and an alpha of 0.03. If the true percentage of agreement is 97% then there is a 22% chance of stopping early for efficacy, and if the true percentage of agreement of 90% then there is a 57% chance of stopping early for futility. The total sample size of 100 lesions was calculated based on a single stage A'hern design with $p_0 = 0.9$ and $p_1 = 0.97$, and the overall power and alpha has been calculated based on exact binomial probabilities.

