12.2 INTERIM AND FINAL ANALYSIS

The interim analysis will be conducted once both of the following conditions are met:

- At least 50 lesions have been identified on [¹²³I]mIBG planar scintigraphy. These lesions will have been identified as positive by a Nuclear Medicine physician at the investigational site.
- A minimum of 9 evaluable patients have completed the study.

The analysis will be done using all identified lesions from at least 9 patients. Therefore, the total number of lesions is expected to be more than 50. The number of lesions identified on [¹²³I]mIBG planar scintigraphy will be reported to the CSM at the CDD at the time of sponsor authorisation of the supply of the [¹²⁴I]mIBG tracer from the manufacturing organisation to the investigational site. The CSM will communicate to the observers and the statistician when the conditions have been met to trigger the interim analysis.

The interim analysis will assess the primary endpoint by comparison of the number of positive lesions detected on [¹²³I]mIBG planar scintigraphy and [¹²⁴I]mIBG PET/CT in order to compare the two modalities. The imaging data will be analysed and scored separately by an agreed number of observers using the same scoring method as described in Section 9.1 in order to prevent subjective bias. Observers may perform their assessment of study imaging data prior to the interim and final

analyses in batches but will remain blinded to the scores of the other observers until the interim and final analyses are triggered and they meet to perform the consensus reviews. Assessment of the reported safety data will be performed at the interim review and will be considered as part of the decision whether to continue recruitment. The feasibility of recruitment of the required minimum number of patients will also be considered in this decision.

The final analysis will be conducted after one of the following conditions is met:

- The study is terminated early
- The end of trial as defined in Section 11 has been reached.

Following lesion detection the agreed number of experienced observers will also perform a semi-quantitative assessment of [¹²⁴I]mIBG PET/CT scans and [¹²³I]mIBG imaging employing SUVmean and SUVmax. The level of disease involvement will be assessed using the International Society of Paediatric Oncology Europe Neuroblastoma (SIOPEN) scoring method and the Curie scoring method (see Appendix 5).

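### The interim stopping rule in protocol 1.2 and 3.3 differs from the tests in 12.1, for futility at 45 of 50 and for efficacy from 54 lesions, and SAP 1.4 and 4.2.1 name the wrong scan for the 50-lesion count

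*Combined protocol and SAP*

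**What the plan says.** **Futility.** Protocol 1.2 and 3.3 say that if the number of lesions also identified on PET/CT "is less than 45 out of 50 the trial will be stopped early for futility". Protocol 12.1 defines the rule as an exact one-sided binomial test of P ≥ 97% at 0.05 and adds: "With a total of exactly 50 lesions this will occur if 45 or fewer lesions are also positive on [¹²⁴I]mIBG PET/CT". SAP 1.4 gives the same cut-off, and SAP 4.2.1 and SAP 5 repeat the test.

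**Efficacy.** Protocol 1.2 and 3.3: "If all lesions (e.g. 50 out of 50) were also identified using [¹²⁴I]mIBG PET/CT the trial may be stopped early for efficacy". Protocol 12.1 uses an exact one-sided test of P ≤ 90% at 0.025, and gives 50 of 50 as its cut-off at 50 lesions. Protocol 12.2 says that "the total number of lesions is expected to be more than 50".

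**Which text governs.** Section 11 ends the trial when "it is confirmed the trial is to stop due to futility as per Section 12.1", and refers the efficacy stop to the same section. Protocol 1.2 and 3.3 do not refer to 12.1 for the stopping rule.

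**Which scan supplies the 50 lesions.** Protocol 1.2, 3.3 and 12.2 and SAP 1.3 say ¹²³I planar scintigraphy; protocol 12.1 and SAP 5 say ¹²³I mIBG. SAP 1.4 says ¹²³I mIBG PET/CT. SAP 4.2.1 says ¹²⁴I mIBG PET/CT.

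**Operating characteristics.** Protocol 12.1: "Overall this design has 82% power and an alpha of 0.03", and "if the true percentage of agreement of 90% then there is a 57% chance of stopping early for futility". It also quotes a 22% chance of an early efficacy stop at true 97%. The lesion counts are minima: "The second stage will end when an overall total of at least 33 patients with at least 100 lesions have been recruited".

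**The concern.** The synopsis and the design section each state a complete stopping rule that is not the one in the statistical section. At exactly 45 of 50 the two rules give opposite decisions. From 54 interim lesions, a result with one discordant lesion permits an efficacy stop under 12.1 but not under 1.2 and 3.3.

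The SAP wording on the scan type matters because the lesion count triggers the interim. Counting on the experimental scan, as SAP 4.2.1 literally says, could bring the interim at a different time from counting on the comparator.

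Finally, 12.1 and SAP 1.4 quote power, alpha and stopping probabilities without saying that they hold only at exactly 50 and 100 lesions, although both counts may be exceeded.

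**Working it through.** **Inputs (protocol 12.1).** p0 = 0.90, p1 = 0.97; futility test at 0.05; efficacy and final tests at 0.025; lesions independent, as the plan assumes. X ~ Bin(n, p), with P(X ≤ k) = Σ C(n,x) pˣ(1−p)ⁿ⁻ˣ summed over x ≤ k.

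**1. Reproduce the plan's figures at 50 then 100 lesions.** Stop for futility at X₁ ≤ 45, stop for efficacy at X₁ = 50, otherwise succeed if the total is ≥ 96 of 100.

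P(success) = P(X₁ = 50) + Σ P(X₁ = x)·P(X₂ ≥ 96 − x) over x = 46 to 49, with X₂ ~ Bin(50, p).

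- Alpha at p = 0.90: 0.0266 (quoted 0.03).
- Power at p = 0.97: 0.8215 (quoted 82%).
- Efficacy stop at 0.97: 0.97⁵⁰ = 0.218 (quoted 22%).
- Futility stop at 0.90: 0.569 (quoted 57%).

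The two-stage figures here and below assume that every permitted efficacy stop is taken.

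**2. Which futility cut-off fits?**

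| Cut-off at 50 lesions | P at 0.97 (must be ≤ 0.05) | P at 0.90 (quoted 57%) |
|---|---|---|
| ≤ 44 (fewer than 45) | 0.0037 | 0.384 |
| ≤ 45 | 0.0168 | 0.569 |
| ≤ 46 | 0.0628 | 0.750 |

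The 0.05 test rejects at 45 and not at 46, and only ≤ 45 gives 57%. The disputed result, exactly 45 of 50, has probability 0.185 at true 90% and 0.013 at true 97%.

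**3. What follows if the trial continues from 45 of 50?**

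- 100 final lesions: 96 are needed, but at most 45 + 50 = 95 are possible. Success is impossible, so alpha and power are the same under both wordings.
- 113 lesions: 109 are needed (108/113 has p = 0.0255), but at most 45 + 63 = 108 are possible. Success is impossible.
- 114 lesions: 109 suffices (p = 0.0239), so all 64 further lesions must match. At true 97% this has probability 0.97⁶⁴ = 0.14.
- 150 lesions: 143 are needed, so 98 of the next 100. At true 97% this has probability 0.42.

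Over the whole design at 50 then 150 lesions, alpha is 0.0177 (≤ 45) against 0.0181 (< 45), and power 0.913 against 0.918. The final totals above 100 are illustrative.

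**4. Efficacy above 50 lesions.** With one miss, P(X ≥ n−1 | 0.90) = 0.9ⁿ + n(0.1)(0.9)ⁿ⁻¹. This is 0.0259 at n = 53 and 0.0237 at n = 54, so the two rules agree from 50 to 53 lesions and part at 54. Chance at true 97% that an efficacy stop is permitted:

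| Interim lesions (illustrative) | All must match | Exact 0.025 test |
|---|---|---|
| 50 | 0.218 | 0.218 |
| 54 | 0.97⁵⁴ = 0.193 | 0.515 (53/54) |
| 60 | 0.97⁶⁰ = 0.161 | 0.459 (59/60) |

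**5. Overall alpha at other permitted counts under the 12.1 tests.** 0.0266 at 50/100, 0.0393 at 54/100, 0.0414 at 54/127, 0.0205 at 80/150. Over 50 to 99 interim lesions and 100 to 200 final lesions it runs from 0.012 (53/113) to 0.041 (54/127).

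**6. Scan labels.** ¹²³I mIBG PET/CT, as in SAP 1.4, is not a modality of this trial. The SAP 4.2.1 label conflicts with the ¹²³I count in SAP 1.3 and SAP 5. The endpoint's denominator is unaffected, because SAP 4.2.1 defines it as the sum of n₁₂₃.

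**The case against.** The futility texts differ only at exactly 45 of 50, and Section 11 sends both early stops to 12.1. SAP 1.4 carries the 12.1 cut-off, and SAP 4.2.1 and SAP 5 repeat its tests. The effect on alpha and power is nil at 50/100 and slight at 50/150. All of this is true and limits the practical risk, but it leaves a wrong threshold in the synopsis and the design section.

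On efficacy, both versions say that the trial may stop, and they agree up to 53 lesions. The difference is therefore in when a discretionary stop is available, not in a required decision. That also stands, but 12.2 expects more than 50 lesions, so counts of 54 and over cannot be dismissed.

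On the scan type, SAP 1.3 and SAP 5 tie the trigger to ¹²³I mIBG, SAP 6 refers to SAP 5, and 12.2 sets out how the site's planar count is reported. The labels in SAP 1.4 and 4.2.1 read as slips. That is a fair description, and they still need correcting.

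On operating characteristics, 12.1 attaches each cut-off to its count, so a careful reader could infer that the figures belong to 50/100. Alpha can also be lower than quoted, not only higher, and 54/127 is the maximum of the grid examined. A sentence added to the plan should therefore state the stopping assumption and not suggest that alpha only rises.

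**Conclusion.** The concern holds, and the text is wrong as written. Fewer than 45 of 50 in 1.2 and 3.3 contradicts the plan's own test and its own 57%. Requiring all lesions to match departs from the 12.1 test from 54 lesions. SAP 1.4 and 4.2.1 misname the scan for the lesion count.

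The local effect is clear: at true 90% there is an 18.5% chance of landing on the disputed 45/50. The effect on overall error rates is small, and the route through Section 11 and the SAP reduces the risk of a wrong decision. The missing qualifier on the operating characteristics is a lesser point. This should be fixed, but it does not undermine the design. All figures assume independent lesions.

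**What to change.** - **Protocol 1.2 and 3.3:** replace both stopping sentences with: *Both early stops are decided by the exact one-sided binomial tests in Section 12.1 at the actual number of lesions. At exactly 50 lesions the trial stops for futility at 45 or fewer and may stop for efficacy at 50 of 50.*
- **SAP 1.4 and 4.2.1:** describe the 50 lesions as positive on ¹²³I mIBG planar scintigraphy.
- **Protocol 12.1 and SAP 1.4:** add: *The quoted power, alpha and stopping probabilities apply at exactly 50 interim and 100 final lesions. At other permitted counts overall alpha differs; it may be lower, and can reach about 0.04 if every permitted efficacy stop is taken.*

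The cost is a wording correction in five sections. The tests, sample size, data collected and analysis code do not change.
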